Full Body Skin Assessment. Study nurses will perform a full body skin assessment for skin irritation or open areas on infants prior to each bath. Following each bath, bedside nurses will conduct a full body assessment every 12 hours for the duration for the study (with the last assessment performed 36 hours after the last bath or prior to discharge- whichever occurs first). Full body assessment for altered skin integrity will be documented on the CHG Skin Assessment Log (Appendix D) provided for each participant. Full body assessment revealing untoward or adverse findings will also be recorded on the CHG Adverse Event Reporting Tool- Alteration in Skin Integrity (Appendix E) and reported to the PI.

CHG Measurement. Serum CHG levels will be quantified weekly by a clinical chemistry fellow with expertise using High Performance Liquid Chromatography coupled with tandem mass spectrometry (LC-MC/MS). Briefly, CHG will be extracted from 200uL of serum following deproteinization with 0.1% formic acid and addition of a deuterated CHG internal standard. Reversed phase HPLC separation and elution will be performed using a Waters Acquity® UPLC system with a C18 column. Detection and quantification will be achieved on a Waters Quattro™ triple-quadrupole mass spectrometer by electrospray ionization in positive ion mode (Chapman, et al 2013).

CHG blood levels. CHG blood level assays will be performed to determine CHG levels in study participants; but will not be used to inform clinical decision-making since safe blood levels of CHG are not known. Thus CHG blood level assays will not be used as the primary method of determining adverse reactions.

Instead, we will employ the current standard of care for determining adverse reactions to topically applied CHG, which is the visual and clinical assessment of nursing and medical staffs for symptoms of an adverse reaction. In this study, visual and clinical assessments for symptoms of an adverse reaction will serve as our primary measure for safety.

We plan to examine associations between CHG blood levels and other adverse reactions (skin irritation or open areas, abnormalities in liver and renal function tests) to help determine safe blood levels in infants 36 weeks PMA or older and less than 48 weeks PMA. Clinical decisions regarding potential reactions will be based on the evidence of adverse events from the visual and clinical assessments for symptoms of an adverse reaction.

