Presently, there are no certified calibrators or standards available for CHG blood levels. Complete validation of the assay for CHG blood levels for use in clinical decision-making would require significant regulatory processes. This would include comparing our assay to those in the literature so that any clinical decision points could be established based on the published in vitro and in vivo data.

In this study, analysis of CHG blood levels will be conducted using a liquid chromatography-mass spectrometry system in the Department of Lab Medicine, assay development laboratory at Boston Children's Hospital. The developed assay for CHG blood levels will not be conducted under the CLIA accreditation of the laboratory and is for research use only (RUO). As such, data from this assay cannot be used for individual patient decision-making (such as discontinuing CHG exposure).

Assay from our laboratory will allow us to measure CHG at 5 ng/mL or even lower; providing greater detail and understanding of the kinetics of absorption and elimination. This is comparatively better than most studies in the literature. In the majority of published studies, CHG in the blood was not quantifiable since the lower limits of quantification, for their instruments, was 20 ng/mL.

If validation were to be conducted using the available instrumentation in the main clinical laboratory, which would allow clinical decision making from individual results, the current clinical mass spectrometers would perform similar to those in the literature. They would be unable to detect CHG in many samples due to insufficient limits of quantification. This is because these clinical laboratory instruments are a generation behind that in the assay development laboratory.

Moreover, utilizing the assay development laboratory will also allow greater flexibility regarding when analyses can be conducted for this study. Testing in the assay development laboratory is more flexible from timing and cost perspectives, and will be conducted weekly based on sample availability; as opposed to the fixed schedule in the main clinical laboratory.

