Although iatrogenic anemia is unlikely to result from participating in this study our patient population is at risk for the development of anemia from a number of potential contributors including: blood loss sustained from invasive procedures such as surgery, low iron stores, bone marrow suppression or intracranial hemorrhage. This warrants monitoring for anemia during the course of this investigation. For the purpose of this study anemia is defined as HCT \leq 28% with respiratory support (mechanical ventilation, continuous positive airway pressure or high flow nasal cannula with FiO₂ > 25% or Oxygen by nasal cannula > 1 liter/min) or HCT \leq 25%: no respiratory support. To monitor infants for the development of anemia during the study, we will be obtaining weekly HCT levels on infants that do not have a weekly HCT levels documented in their medical record. A plan for the management of infants with anemia has been put in place and is outlined later in this protocol under Table 1: Management of Adverse Events to CHG Baths.

Data Collection. Data collection will be performed by study nurses in the NICU and pediatric CICU. Data collection procedures by the study nurses will consist of:

1. Assigning study ID numbers.
2. Recording bi-weekly CHG baths on the CHG Bath Data Collection Tool.
3. Maintaining an on-line password protected database that will be used to record participants CHG blood levels, AST, ALT, HCT, serum Creatinine and untoward/adverse skin events and CLABSI's.
4. Recording the incidence and severity of untoward/adverse skin reactions and adverse events experienced by study subjects on the CHG Adverse Event Reporting Tool-Alteration in Skin Integrity or CHG Adverse Event Reporting Tool-Events Not Related to Skin (Appendix I).
5. Maintaining a computerized log to track the development of skin reactions, elevated CHG and other blood levels, anemia and hours/days of onset of adverse event from time study initiated.
6. Maintaining a computerized log of all CHG levels (this will be maintained by the study personnel in the laboratory).

The study PIs will be responsible for following up on adverse events and contacting the Data and Safety Monitoring Committee (DSMC) for consultation.

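### Study nurses who grade skin before each bath also keep the records of CHG levels, with no blind described, so a known level could bias the exploratory link between level and skin reaction

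*Combined protocol and SAP*

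**What the plan says.** Two groups look at the skin. Under Full Body Skin Assessment, "Study nurses will perform a full body skin assessment for skin irritation or open areas on infants prior to each bath", and after each bath "bedside nurses will conduct a full body assessment every 12 hours for the duration for the study".

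Under Data Collection, "Data collection will be performed by study nurses in the NICU and pediatric CICU". Four items in that task list matter here:

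- Item 3: "Maintaining an on-line password protected database that will be used to record participants CHG blood levels, AST, ALT, HCT, serum Creatinine", with skin events held in the same database.
- Item 4: recording how often skin reactions occur and how severe they are, on the adverse event reporting tools.
- Item 5: "Maintaining a computerized log to track the development of skin reactions, elevated CHG and other blood levels, anemia and hours/days of onset".
- Item 6: "Maintaining a computerized log of all CHG levels (this will be maintained by the study personnel in the laboratory".

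The section CHG blood levels states the use to be made of these data: "We plan to examine associations between CHG blood levels and other adverse reactions". The reactions named are skin findings and abnormal liver and renal tests, and the aim is to inform what level is safe at this age. The same section makes visual and clinical assessment the primary safety measure. It also says the assay is for research use only: "data from this assay cannot be used for individual patient decision-making (such as discontinuing CHG exposure".

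In Table 1, mild redness seen once needs no action. Mild redness seen twice, redness that persists up to the second bath, or moderate redness leads to discontinuation of baths, unless confined to the diaper area.

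No section withholds CHG levels from those who assess or grade the skin.

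**The concern.** Whether redness is mild or moderate, or has persisted, is a judgement. An assessor who knows that an infant's last level was high may look harder or grade up, and one who knows it was undetectable may do the reverse. Either would create or strengthen an association between level and reaction without any true one, and that association is what the pilot would use to say something about safe levels.

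There is a second consequence. Because the grade decides whether baths stop, knowledge of the level at grading is an indirect route by which a research-only result could influence a decision that the plan says it must not inform.

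The bath cannot be masked in a single-arm study, but the level can be.

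**Working it through.** The plan gives no figure to reproduce. The check is a tracing of roles and timing, with two small calculations.

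**1. Do the roles overlap?** Yes. Study nurses do the pre-bath check (Full Body Skin Assessment), record severity (item 4), and keep CHG levels in a database and a log that also hold skin events (items 3 and 5). CHG Bath Intervention names five trained study nurses per unit, so the pool is small.

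**2. Are levels known while infants are followed?** Probably, by someone. Assays are run weekly (CHG Measurement). The holding rules for adverse events and for clinical instability call for two further CHG levels unless the previous one was undetectable, which requires knowing the previous result. The CHG Lab Work Log records blood levels and is also used throughout participation to track blood volume. The plan does not say when a result reaches a study nurse.

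**3. What share of skin checks is open to this?**

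- Bedside nurses: 7 × 24 / 12 = 14 per week.
- Study nurses: 2 per week (Monday and Thursday).
- Study-nurse share: 2 / (14 + 2) = 12.5%.

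Severity entries under item 4 come on top of this and could carry more weight than 12.5% suggests.

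**4. How many pre-bath checks can follow a post-bath result?** CHG is sampled on Fridays. Count days from the first bath (day 0). Assume either that each result is known by the next bath (worst case) or that it takes 7 days. The baseline level is left out because it precedes the study baths.

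| First bath | Later pre-bath checks to day 12 | First Friday sample | Checks after result, worst case | Checks after result, 7-day lag |
|---|---|---|---|---|
| Monday | days 3, 7, 10 | day 4 | 2 (days 7, 10) | 0 (result day 11) |
| Thursday | days 4, 7, 11 | day 1 | 3 (days 4, 7, 11) | 1 (day 11, result day 8) |

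Day 12 is close to the mean NICU stay of 12.7 days in Setting, where the CICU average is 9–15 days. Infants who stay longer, up to 12 weeks, contribute more checks.

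**5. What could it do to the association?** This is an illustration only, and the detection probabilities are assumptions. Suppose there is no true association. A reaction is detected with probability d1 = 0.90 when the level is known to be high and d0 otherwise. The apparent risk ratio is d1/d0 if every grading is affected. If only a share w = 2/16 is affected and gradings carry equal weight, it is [w·d1 + (1 − w)·d0]/d0.

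| d0 | All gradings affected | Only 2 of 16 affected |
|---|---|---|
| 0.80 | 1.125 | 1.02 |
| 0.70 | 1.29 | 1.04 |
| 0.60 | 1.50 | 1.06 |
| 0.50 | 1.80 | 1.10 |

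With assessors blind to levels, the ratio is 1.00 in every row.

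**The case against.** The strongest reply is that the documents do not show a level reaching the grader before the grading. Release timing is not given. Item 6 sits in the study nurses' list yet belongs to laboratory staff, so the list is not wholly literal. Data Management and Quality Control gives all data management to a nursing research group and defers procedures to a manual of operations. Nothing says that the nurse who keeps the log also grades the same infant. These points stand as limits: the route is open, but not shown to be used.

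Bedside nurses do most of the checks and are not shown to see CHG levels, and the CHG Erythema Assessment Tool supports consistent grading. Both reduce the effect. The tool is not a blind, however, and the audits described concern bathing technique, not grading.

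The association is also exploratory. Data Analysis plans descriptive statistics and plots for levels, and rules out hypothesis tests when characterising the infants with adverse events. The part that relates CHG to liver and renal tests cannot be altered by a nurse's grading.

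Four stronger readings are tempting, and the documents do not support them.

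- *All 50 infants are affected.* Short stays, Friday sampling and unknown release timing mean that some infants may have no pre-bath check after a post-bath result.
- *One changed grading is a known share of the events.* Hypothesis 1 requires a rate below 10%, which is at most 4 of 50 infants because 5/50 is exactly 10%. That counts any adverse event, including the laboratory findings in Table 1, so it gives no denominator for skin events.
- *The assay will decide who stops baths.* The plan bars this. Only an indirect influence through grading is possible.
- *The blind would be free.* It requires reporting to be rerouted and data entry to be reassigned.

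**Conclusion.** The point holds in a limited form. Study nurses both grade skin and keep CHG levels, no blind is described, and the plan means to relate the two. A level known before a later grading could bias that association and bear indirectly on grading that stops baths.

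The exposure is about 2 of 16 scheduled weekly checks plus the severity entries, and only those made after a result is released. The size of the bias cannot be computed from the documents, and the risk ratios above rest on assumed detection probabilities. The overall adverse event proportion and rate would move only if knowledge of levels shifted grading up or down overall, which nothing in the documents shows.

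This is a cheap improvement worth making before enrolment, not a flaw that undermines the primary estimate.

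**What to change.** - In Data Collection, remove CHG levels from items 3 and 5 of the study nurses' tasks. Keep AST, ALT, creatinine and HCT, which Table 1 acts on.
- Record only CHG sample collection and volume, not the result, on any CHG Lab Work Log that skin assessors can see.
- Hold CHG results in the laboratory log (item 6) and merge them into the study database after the infant's last skin assessment.
- Have the laboratory send levels straight to the DSMC for the reviews in the Data Safety Monitoring Plan, in place of the PIs' summary for that item.
- For the extra levels under the holding rules, have the laboratory tell the team only whether a sample is needed. The rule itself does not change.

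The cost is a change of data flow using a log and staff already in the plan: rerouted reporting, some reassigned data entry, and no real-time view of individual CHG levels for the study team, which the plan already bars from individual decisions. A small leak remains, because the sample message reveals whether the previous level was detectable. After an adverse-event hold, the event has by then been graded and the baths suspended, although symptom follow-up continues. After an instability hold bathing may resume, so there the message could precede later checks.

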CHG will be safe for use in a sample of infants 36 weeks PMA or older, and less than 2 months of age (48 weeks PMA) with a CVC as evidenced by an adverse event rate less than 10%.

Research Question 2:

Does twice weekly CHG baths lead to rising (cumulative) CHG blood levels, liver function tests (LFTs -AST/ALT) and Serum Creatinine over time in a sample of infants 36 weeks PMA or older, and less than 2 months of age (48 weeks PMA) with a CVC?

Hypothesis 2:

Twice weekly CHG baths do not lead to rising (cumulative) CHG blood levels, LFTs (AST/ALT)

and Serum Creatinine over time in a sample of infants 36 weeks PMA or older, and less than 2 months of age (48 weeks PMA) with a CVC.

Methods

Study Design: A pilot study using a single arm trial design.

Study Sample: Our convenience sample will include 50 infants. Infants admitted to the NICU or pediatric CICU will be eligible to participate.

Inclusion criteria.

- Greater than/equal to 36 weeks PMA (gestational age + chronological age)
- Less than/equal to 48 weeks PMA (gestational age + chronological age)
- Greater than/equal to 3 days of age
- Existing or soon to be placed, peripheral or surgical CVC
- Permission to participate in trial by attending physician
- Parent or legal guardian informed consent to participate in the trial

Exclusion criteria.

- Infant with a large open lesion or severe skin condition (i.e., Myelomeningocele, Gastroschisis, lymphatic malformation, open chest, ostomies and/or mucus fistulas or Icthyosis)
- Infants with active seizure disorders
- Infants with Hypoxic Ischemic Encephalopathy
- Infants with severe multi-system organ failure or Liver failure as defined by documentation of abnormal liver function tests: alanine aminotransferase (ALT) and aspartate aminotransferase (AST) Gamma-glutamyltransferase (GGT) and L-lactate dehydrogenase (LD).
- HCT \leq 28%: Respiratory support (mechanical ventilation, continuous positive airway pressure or high flow nasal cannula with FiO₂ > 25% Oxygen by nasal cannula > 1 liter/min) or HCT \leq 25%: No respiratory support.
- Infant with renal impairment as defined by: documented serum Creatinine greater than 0.7, renal disorders (renal agenesis, polycystic kidney disease, dysplastic kidneys, acute renal injury).
- Infants deemed clinically unstable by their physician such as patients that are extremely fragile and wouldn't tolerate the stimulation of the bathing process or those infants being considered for withdrawal of care.

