Assessment of Liver and Renal Function. Most drugs or chemicals are excreted from the body via the hepatic or renal systems. Therefore, standard LFTs, namely AST and ALT, and the Serum Creatinine levels will be monitored on all subjects. If these labs have been obtained as part of the standard of care, the results will be used by the study team and not repeated in order to minimize additional blood loss or iatrogenic anemia. However, if the study subject's diagnosis did not warrant monitoring of these labs, they will be obtained weekly with the CHG blood level.

Procedures for Obtaining CHG, ALT, AST and HCT levels. A single CHG level will be obtained at baseline and then weekly on Fridays for the remainder of the study for each study participant. Every Friday additional labs will be obtained to monitor liver and renal function (AST, ALT, Serum Creatinine) and HCT for anemia.

Often these lab values are obtained as part of routine care in the ICU. If these labs have not been obtained, they will be added to the weekly labs that will require an additional 1.0 mLs. The study personnel performing the bath will assess the need for the additional labs and notify the bedside nurse so that these labs can be obtained at the appropriate time as per the CHG Study Research Order (Appendix F). The study labs will be drawn with other lab work via central line whenever possible. If no other lab work is scheduled to be obtained, or if the central line gauge is too small (less than 2.6 Fr), then the labs will be obtained at the designated time by heel stick. When no other lab work is to be obtained, infants will need 1-2 heel sticks per week for a required sample of 1- 1.5 mLs in order to limit access of CVC and minimize risk of infection. Standard heel sticks are safely performed on patient care units using the lateral aspect of the infants' pre-warmed heel. Blood levels will be recorded on the CHG Lab Work Log (Appendix G) and entered into a computerized database. Lab specimens for this study will be tracked by utilizing a CHG Study Lab Requisition Form (Appendix H) that bears the patients study ID number followed by a unique specimen identifier (i.e. Patient ID "#CHG001" followed by unique lab identifier "3456").

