Assessment for Iatrogenic Anemia. CHG levels being obtained for this study require 0.5mL for each sample. The volume of blood for the ALT/AST/ Serum Creatinine level is 0.5 mL and the hematocrit (HCT) is 0.5mls. The minimum total blood volume obtained per week will be 0.5 mL, and the maximum total blood volume obtained per week will be 1.5 mLs. If a study participant were to remain in the study for the maximum length of time (12 weeks) the maximum amount of blood obtained for the study will be 18 mLs (0.5mL at baseline, 1.5 mL weekly for CHG levels, ALT, AST, serum creatinine and HCT). If the HCT and Serum Creatinine have already been obtained as part of the infant's routine ICU bloodwork as is often the case (and not for the study), the maximum blood obtained for the study is 12.5 mLs (0.5mL at baseline, 1 mL weekly for CHG levels, ALT, AST).

To put this in perspective, the average blood volume for a full term or near term newborn is 80mL/kg (160 mL for a 2 Kg infant). Infants born at 36 weeks gestation, weigh between 2.5-3.5 Kg with an average weight of approximately 2.8 Kg, thus their estimated blood volume is 224 mLs. Iatrogenic

anemia occurs when blood loss exceeds 20 % in a 48-hour period (44.8 mL in a 2.8 Kg infant). Thus, it is unlikely that an infant would sustain iatrogenic anemia from participating in this study. However, blood volume removed will be maintained on the CHG Lab Work Log for each study subject throughout study participation (in order to monitor blood volume removed for study lab work). If the study labs are consistently added on to the study subject's routine lab work, and thought to pose an additional clinical risk in terms of blood loss, the DSMC and the FDA will be notified.

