Does twice weekly CHG baths lead to rising (cumulative) CHG blood levels, liver function tests (LFTs -AST/ALT) and Serum Creatinine over time in a sample of infants 36 weeks PMA or older, and less than 2 months of age (48 weeks PMA) with a CVC?

Data Analysis 2:

Descriptive statistics including mean, median, range and frequencies will be used to describe CHG, LFTs and serum Creatinine blood levels over time. We will examine scatterplots and other graphical analysis of blood level dispersion over time to look for relationships.

Sample Size Justification. The primary quantitative goal of this study is estimation of the adverse event rate per 100 patient days. The study sample size will impact the precision of this estimate, and we will establish an upper bound on the rate if zero adverse events occur. In this context, we designed the study sample to expand the existing knowledge base.

Based on recent safety data (Quach, et al 2014) on roughly 200 neonates which recorded no adverse events, we assume the rate of adverse events using CHG bath is lower than 5 events per 1000 days of post-exposure follow-up. We propose following N=50 subjects over 7 days of post-exposure follow-up, for a total of 350 observation days. Assuming rates of 3.5 events or 1.0 events per 1000 days of follow-up, the probability that at least one subject will experience an adverse event is roughly 83% or 40% respectively. Using Monte Carlo simulations, the mean upper bound for estimable rates is 5.5 events per 1000 days.

Auditing and Inspecting:

The sponsor-investigator will permit study-related monitoring, audits, and inspections by the Boston Children's Hospital IRB, the independent data monitor and government regulatory bodies, of all study related documents (e.g. source documents, regulatory documents, data collection instruments, study data etc.). The Investigator will ensure the capability for inspections of applicable study-related facilities.

Human Subjects:

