BCH Committee for Clinical Investigation approval will be obtained before study procedures commence. All study staff will be Citi-program trained. Informed consent/HIPPA forms will be secured before initiation of any study procedures. A computerized database to track subjects through the research continuum will be developed and housed on a password-protected site behind the BCH firewall. Subjects will be assigned study ID numbers that will appear on all study materials and that will be utilized in place of subjects' names in the computerized database. A separate (electronic) CHG Study ID Assignment Log linking subject's names and ID numbers will be maintained by study personnel and kept in a locked cabinet behind a locked door. Only approved study personnel will have access to the log.

This study is considered greater than minimal risk with a potential for direct benefit. There is strong evidence that CHG will help prevent HAIs, however the safety profile for using CHG in infants less than 2 months of age (48 weeks PMA) is not known. To monitor for adverse events, the study team has developed a Data Safety Monitoring Plan (DSMP) and adverse event management plan (see Table 1). Adverse events to CHG baths include mild to severe skin lesions and possible absorption of CHG into the blood that could result in more serious problems such as respiratory, renal and liver problems or anaphylaxis. Thus the study team is taking a conservative approach. In an attempt to usurp the benefits associated with CHG while concurrently minimizing the likelihood of adverse events, study subjects will receive twice-weekly, instead of daily, CHG baths.

While these baths still place the subjects at risk for adverse events we believe twice-weekly baths will minimize these risks. To monitor for adverse events the study team has developed the following procedures:

1. Study RNs will perform a full body skin assessment for skin irritation or open areas prior to each bath.
2. Bedside RNs will complete skin assessments every 12 hours during the course of the study.
3. A plan is in place for Management of Adverse Events to the CHG Baths. (Table 1.)
4. To monitor for absorption into the blood, infants will have blood levels (CHG, ALT, AST, and Serum Creatinine) drawn at baseline and weekly and when an infant is removed from the study in response to an adverse event. In addition, infants will be monitored weekly for the development of iatrogenic anemia.

Data Safety Monitoring Plan:

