Holding rules for patients with anemia requiring blood transfusion. All study participants that require a blood transfusion while enrolled in the study will have CHG baths suspended until 1-week post transfusion and will have a pre- and post-transfusion assessment of vital signs (ranges-heart rate, respiratory rate, blood pressure, oxygenation requirement and means of respiratory support). A post-transfusion hematocrit will also be obtained, if not attained via standard of care, and documented on the CHG Blood Transfusion Tool (Appendix N). The CHG baths will resume 1-week post transfusion if study participant is deemed stable by both the study and medical teams.

Study participants that do not receive a blood transfusion or are deemed not stable will have monitoring of daily vital signs (ranges-heart rate, respiratory rate, blood pressure, oxygenation requirement and means of respiratory support), HCTs that are obtained as routine ICU care, and significant changes to clinical status for 1 month from cessation of CHG baths or until discharge, whichever comes first to assess for adverse events related to anemia.

Stopping rules for patients with anemia requiring blood transfusion. All study participants that have had CHG baths suspended and that do not receive a blood transfusion or are deemed unstable will be removed from the study after completing the clinical monitoring as described above.

Adverse Event (Other Than Anemia):

Holding rules for patients that experience an adverse event: All study participants that experience an adverse event, as described in table 1, and have CHG baths suspended due to the adverse event will have 2 CHG levels obtained within 1 week of CHG bath (recorded on CHG Lab Work Log), unless the previous level was not detectable. These infants will also have monitoring for adverse event symptom resolution and daily vital signs (ranges-heart rate, respiratory rate, blood pressure, oxygenation requirement and means of respiratory support) for 1 month from cessation of CHG baths or until discharge, whichever comes first.

Stopping rules for patients that experience an adverse event. All study participants that have CHG baths suspended due to an adverse event will be removed from the study after completing the clinical monitoring as described above.

Clinical Instability:

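### Research Question 2 asks whether levels rise with repeated baths, but Data Analysis 2 commits to no within-infant summary, so a rise confined to a minority of infants could be missed

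*Combined protocol and SAP*

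**What the plan says.** Hypothesis 2 begins "Twice weekly CHG baths do not lead to rising (cumulative) CHG blood levels, LFTs (AST/ALT" and goes on to serum creatinine. Data Analysis 2 answers it in two sentences: "Descriptive statistics including mean, median, range and frequencies will be used to describe CHG, LFTs and serum Creatinine blood levels over time" and "We will examine scatterplots and other graphical analysis of blood level dispersion over time to look for relationships". The only intervals in the Data Analysis section are for the two adverse event measures.

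The data are repeated measures. Under the procedures for obtaining labs, "A single CHG level will be obtained at baseline and then weekly on Fridays for the remainder of the study for each study participant", and "Every Friday additional labs will be obtained to monitor liver and renal function (AST, ALT, Serum Creatinine) and HCT for anemia".

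Time in study varies. Under Study Participation Ends, an infant leaves at 48 weeks PMA (12 weeks at most), at discharge or transfer, or when the CVC is removed. Table 1 also stops baths when AST exceeds 70, ALT exceeds 60 or creatinine reaches 0.7. The stopping rules then remove the infant after a monitoring period. CHG levels trigger nothing, because the assay is for research use only.

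On the baseline draw the sections differ. Human Subjects, item 4, says that "infants will have blood levels (CHG, ALT, AST, and Serum Creatinine) drawn at baseline and weekly and when an infant is removed from the study". The lab procedures name only a CHG level at baseline. The blood budget under Assessment for Iatrogenic Anemia allows "0.5mL at baseline, 1.5 mL weekly for CHG levels, ALT, AST, serum creatinine and HCT", and 0.5 mL is the volume of the CHG sample alone.

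**The concern.** Accumulation happens inside an infant. A mean or scatter of levels by time compares different infants at different times unless the points are linked. If those who leave differ from those who stay, the trend in the summary mixes real change with a change in who is being measured.

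For AST, ALT and creatinine one part of this is built into the design: the value being studied decides who stops. Taken alone, that pulls later values towards no rise. Staggered exit by discharge or line removal could act in either direction. For CHG only the second mechanism applies.

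At stake is the stated answer to one of the study's two questions, in a pilot meant to support a larger efficacy study. That answer could also disagree with the study's own count of laboratory adverse events.

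**Working it through.** The plan gives no sample size, effect size or SD for Research Question 2, so there is no figure to reproduce.

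**1. How many infants lie behind later values.** Inputs: 50 infants (Study Sample); average stay 12.7 days in the NICU and 9 to 15 days in the CICU age group (Setting). Assumption: exponential time in study. Infants remaining at week w = 50 × exp(−7w / mean stay).

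| Mean stay (days) | Week 1 | Week 4 |
|---|---|---|
| 9 | 50 × exp(−7/9) = 23.0 | 50 × exp(−28/9) = 2.2 |
| 12.7 | 50 × exp(−7/12.7) = 28.8 | 50 × exp(−28/12.7) = 5.5 |
| 15 | 50 × exp(−7/15) = 31.4 | 50 × exp(−28/15) = 7.7 |

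Infants with a CVC may stay longer than these unit averages.

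**2. An AST illustration.** The documents give no laboratory means or SDs, so every input except the 50 infants, the cut-off of 70 and the 12-week limit is assumed. Entry level has mean 40 and SD 12, limited to 70 or less. Within-infant SD is 6. Stay is exponential with mean 2 or 4 weeks and unrelated to AST. Baths stop at the first value above 70, with no labs afterwards. There are 1,500 simulated trials per case. True week-4 change:
- all infants rise, 5 U/L per week on average (SD 4): 4 × 5 = 20;
- a minority rises, 20% at 15 U/L per week: 0.2 × 15 × 4 = 12;
- nobody rises: 0.

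The pooled measure is the week-4 mean minus the baseline mean. This is one reading of levels over time, not a contrast that the plan names. Results are for mean stay 2 / 4 weeks, in U/L.

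| Truth at week 4 | Pooled contrast | Mean change to last on-bath value | Same infants' true change over the same time |
|---|---|---|---|
| 20 (all) | 13.4 / 13.2 | 11.4 / 15.6 | 10.7 / 14.4 |
| 12 (minority) | 1.4 / 1.0 | 5.5 / 6.7 | 5.2 / 6.2 |
| 0 (none) | −0.3 / −0.5 | 0.1 / 0.2 | 0 / 0 |

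The minority rise nearly vanishes from the pooled contrast, because the risers cross 70 and drop out. Linking by infant at a fixed week does not cure this: change from baseline among infants still present at week 4 is 2.0 / 1.8 against 12.

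The minority figure depends on no labs being pooled after the trigger. If labs continue during a hold, levels plateau and the values are pooled, the contrast is 7.4 / 7.5.

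**3. Could a false rise appear?** Suppose nothing rises, but infants with higher AST stay longer (log mean stay +0.5 per 12 U/L of baseline). The pooled contrast is then +7.5 / +4.4. With half that link it is +4.5 / +2.2. Mean change to the last on-bath value is 0.4 / 0.5.

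**The case against.** **This is a single-arm pilot, and a descriptive analysis suits it.** That stands. Research Question 2 has no test or decision rule, and the stated primary quantitative goal is the adverse event rate. Within-infant change is a reading of the hypothesis, although the natural one. The allowance for other graphs could include per-infant plots, but nothing commits to them. The remedy is itself descriptive.

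**A strong laboratory signal is not lost.** That also stands. In the minority case about 3.6 / 6.2 of 50 infants cross 70, against 0.5 / 0.9 when nothing rises. Each crossing stops baths, goes to the PI and prompts a DSMC meeting. Ranges and plots would show the high values too.

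**The within-infant summary is not closer to a fixed-week truth.** Correct. With all infants rising and a 2-week stay it gives 11.4 against 20, further off than the pooled 13.4. It answers a different question: how far each infant moved during its own time on baths. The columns above are not a like-for-like contest.

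**The baseline conflict is weak evidence.** Human Subjects does list these labs at baseline, and the blood budget is loose: 0.5 + 12 × 1.5 = 18.5 mL, not the stated 18. The sections still disagree, and change from baseline depends on the answer.

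A reader might also infer that AST, ALT and creatinine cease during a hold, since infants who "have CHG baths suspended due to the adverse event will have 2 CHG levels obtained within 1 week of CHG bath" have no liver or renal labs listed there. The documents do not say so. The hold rules do not cancel the weekly schedule, and this is a separate drafting matter.

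**Conclusion.** The concern holds as a cheap improvement in method. Data Analysis 2 does not commit to the summary that its question calls for, while the infants behind later values become few and, for AST, ALT and creatinine, are selected partly on the outcome. Read as weekly means, the summaries could hide a rise confined to a minority: about 1 against 12 U/L in the illustration, under assumed AST values and with no labs pooled after stopping. A general rise would show, understated (about 13 against 20).

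Three stronger readings are not supported:
- That the plan will report a false rise. This needs infants with higher values to stay longer, which the documents do not establish.
- That the net bias has a known direction. Stopping at a cut-off and staggered exit can oppose each other.
- That CHG results are distorted by a stated amount. CHG triggers no stopping, so only case mix applies, and every figure here is for AST.

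**What to change.** In Data Analysis 2, make within-infant change the main descriptive summary for Research Question 2:
1. Per-infant profile plots.
2. Change from baseline to the last on-bath value, including any value that triggered stopping, reported with each infant's time on baths.
3. Change from baseline by week, as support.
4. Numbers remaining and reasons for leaving, by week.
5. For AST, ALT and creatinine, time to first crossing of the Table 1 cut-offs.
6. For CHG, a rule for how values below the quantification limit enter the change.

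The lab procedures, the blood budget under Assessment for Iatrogenic Anemia and Human Subjects item 4 must be reconciled on whether AST, ALT and creatinine are drawn at baseline.

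The cost is analysis wording and a little programming. No new data are needed if these labs are drawn at baseline. If they are not, change from baseline exists only for infants with routine-care values, and that number should be reported.

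The report should state two limits. Change to the last on-bath value covers each infant's own, often short, time on baths and does not estimate change at a fixed week; the triggering value also nudges it up slightly. Change by week among infants still present stays biased if only a minority rise.
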